### STAGE 1 STEP 1 Fast-track design (1 patient per dose level)

Start at DL1, enroll 1 patient per DL separated by a minimum of 21 days (DLT period) until the:

- 1st pre-defined adverse event defined as any of the following treatment emergent Grade 2 events lasting >72 hours within 5 days of 1st dose of HCW9218: fatigue, flu-like symptoms or injection site reaction
- and the patient completes the 21 day DLT period with no DLT- Activate Stage 1 Step 2
- 1st DLT event within 21 days after the 1st dose of HCW9218 as defined in the Schema and in Section 6.3 Activate Stage 2 (Stage 1 Step 2 is not used)

  OR
- 9 patients are treated at the DL4 (This completes enrollment Stage 1 Step 2 and Stage 2 are not used)

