# 6.2.1 STAGE 1 STEP 1 - Fast-track design (1 patient per dose level)

Start at DL1, enroll 1 patient per DL separated by a minimum of 21 days (DLT period) until the:

- 1st pre-defined adverse event Any of the following treatment emergent Grade 2 events lasting >72 hours within 5 days of 1st dose of HCW9218: fatigue, flu-like symptoms or injection site reaction.
- And the patient completes the 21 day DLT period with no DLT- Activate
   Stage 1 Step 2 in Section 6.2.2.

OR

1st DLT event within 21 days after the 1st dose of HCW9218 - Activate
 Stage 2 in Section 6.2.3 - Stage 1 Step 2 is not used.

OR

• 9 patients are treated at the DL4 - This completes enrollment - Stage 1 Step 2 and Stage 2 are not used.

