## 13 Statistical Considerations

## 13.1 Study Design, Objectives and Endpoints

The purpose of this Phase I open-label study will be to identify the maximum tolerated dose (MTD) in a combined study group of all solid tumor cancers (except pancreatic cancer) and provide preliminary estimates of the response for future studies.

The primary endpoint is to provide the MTD of HCW9218 in advanced solid tumor cancers. The primary analysis will be intent-to-treat from the point of 1st injection of HCW9218 both for toxicity and efficacy. Patients who discontinue therapy prior to injection #1 will be replaced. We expect that the number of patients coming off therapy prior to injection #1 will be minimal/none.

There are 5 potential dose levels defined for Phase I. The trial will be conducted with no intra-patient escalation. The starting dose will be 0.25 mg/kg HCW9218 with a safety dose of 0.1 mg/kg HCW9218. The subsequent planned cohorts will be 0.5 mg/kg HCW9218, 0.8 mg/kg HCW9218 and 1.2 mg/kg HCW9218 (Table 1). Given that little to no toxicity is expected, the MTD will be determined using an adaptation of the continual reassessment method (CRM) (O'Quigley, 1996) starting with 1 patient cohorts.

Table 1.

Phase I HCW9218 Dose Levels					
Dose Level	HCW9218 dose				
-1	0.1 mg/kg				
1 (start)	0.25 mg/kg				
2	0.5 mg/kg				
3	0.8 mg/kg				
4	1.2 mg/kg				

This Phase I study will be conducted in two consecutive stages (non-CRM and CRM). A minimum of 21 days must separate each cohort. All patients are assessed for Dose Limiting Toxicity (DLT) per Section 6.3 as defined in the schema below:

**Stage 1 Step 1** uses a fast-track design (1 patient per cohort) with a minimum of 21 days between each patient until one of the following occurs:

The 1st occurrence of a **pre-defined treatment emergent adverse event** within 21 days of the 1st HCW injection (Section 6.2.1) at which point the study moves to **Step 2** and the cohort size increases from 1 to 3 patients with 2 additional patients added to the current cohort. A minimum of 21 days must separate each 3 patient cohort

- Escalation in Step 2 continues until the 1st DLT event at which point Stage 2
   (CRM) is activated. If Cohort 4 is completed without a DLT, Stage 2 (CRM) is not used.
- The 1st occurrence of a DLT at which point the study moves directly to Stage 2
  (CRM) as detailed below and Step 2 is not used.

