## 13.3 Sample Size

A maximum of 24 patients will be enrolled with a target DLT rate of ≤25%. Based on the simulations from Table 2, this should be sufficient and safe to define the MTD. Although complete skeleton estimates will not be determined until Stage 2, Table 2 is calculated based on hypothesized values.

Table 2. Operating characteristics for Adaptive-CRM

-	_		•				
	Expected DLT,	Expected	SAE 	Excessive DLT, Excessive SAE			
HCW9218 Dose	True	Prob. of	$N^4$	True	Probability	N	
Levels	Probability	dose 		Probability	of dose		
0.1 mg/kg (-1)	0.5%, 0.5%	0%	0	5%, 18%	3%	3	
0.25 mg/kg (1, start)	0.75%, 1.5%	0%	1	10%, 29%	18%	6	
0.5 mg/kg (2)	1.5%, 3%	0%	1	25%, 50%	44%	9	
0.8 mg/kg (3)	3%, 5%	0%	1	40%, 66%	34%	5	
1.2 mg/kg (4)	7%, 7.5%	100%	9	55%, 77%	1%	1	

- 1. SAE's without a DLT trigger step 2 in stage 1, DLT's regardless of SAE's trigger stage 2
- 2. Expected/Excessive values are the hypothesized true values under the simulation
- 3. Probability of dose chosen as the MTD using the Adaptive-CRM design
- 4. The hypothesized number of patients enrolled at each dose during the trial under the assumed hypothesized "true" probabilities

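### Section 13.1 opens Stage 1 Step 2 at the pre-defined event, while the Synopsis and 6.2.1 wait for that patient's 21-day DLT result; the three texts need one activation rule

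*Combined protocol and SAP*

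**What the plan says.** - **Section 6.2.1** defines the pre-defined events (fatigue, flu-like symptoms, injection site reaction) as "Grade 2 events lasting >72 hours within 5 days of 1st dose of HCW9218". It then adds a second condition: "And the patient completes the 21 day DLT period with no DLT". Only then is Step 2 activated. A DLT within 21 days goes to Stage 2 instead, with Step 2 not used.
- **Synopsis, Stage 1 Step 1** has the same two-part rule: "the patient completes the 21 day DLT period with no DLT- Activate Stage 1 Step 2".
- **Section 13.1** ties the move to the event alone. After naming the first pre-defined event it reads "HCW injection (Section 6.2.1) at which point the study moves to", and the destination named there is Step 2. The enlargement is part of the same instruction: "the cohort size increases from 1 to 3 patients with 2 additional patients added to the current cohort". It attaches no DLT-period condition to that move.
- **Section 13.3, Table 2 footnote 1** gives the branch as "SAE's without a DLT trigger step 2 in stage 1, DLT's regardless of SAE's trigger stage 2". Footnote 2 to the table in Section 10.2 likewise sends the study to Step 2, or to Stage 2 if a DLT also occurs.
- **Section 6.3** keeps the DLT period open until the Cycle 2 Day 1 assessment and laboratory results.
- **Sections 5.3 and 13.1** provide for replacement only of patients who never receive injection 1.

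**The concern.** All the texts agree that a DLT leads to Stage 2 and that an event without a DLT leads to Step 2. The branch therefore cannot be known until the DLT status of the patient with the event is known. Section 13.1 nevertheless acts at the event.

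Nothing else in the plan clearly holds the two added patients back. In 13.1 the 21-day gap between single patients lasts only until the trigger, and the gap that remains is between cohorts. The added patients join the current cohort. The 21-day team review in Section 11.4 confirms timing and dose for the next cohort and does not mention patients added to the present one.

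At stake is whether two more patients can be dosed at a level where the first patient may still have a DLT, and whether site and statistician are following the same rule. A smaller gap sits beside this. No text says how the trigger treats a dosed patient who has the event but whose DLT period cannot be completed.

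**Working it through.** **1. Time left in the DLT window if 13.1 is followed.** The inputs are the 21-day DLT period (6.3), event duration over 72 hours, and the 5-day event window (6.2.1).

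- Earliest: onset at dosing, qualifying 3 days after the dose; 21 − 3 = 18 days left.
- Latest: onset 5 days after the dose, qualifying at 5 + 3 = 8 days; 21 − 8 = 13 days left.
- If the 14-day stagger between first and second patients in Section 3 covers an enlarged cohort: 21 − 14 = 7 days left.

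Section 13.1 itself gives the event window as 21 days while citing 6.2.1. On that reading an event can qualify later and leave less time, down to none.

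**2. How often the order matters.** The inputs are Table 2's DLT and SAE rates. SAE is read as the pre-defined event because footnote 1 makes it the Step 2 trigger. Event and DLT are assumed independent, because Table 2 gives no joint rate. With d the DLT rate and e the event rate, P(both) = d·e and P(neither) = (1 − d)(1 − e).

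| Scenario, level | d, e | Both | Neither |
|---|---|---|---|
| Excessive DL1 | 10%, 29% | 0.029 | 0.639 |
| Excessive DL2 | 25%, 50% | 0.125 | 0.375 |
| Excessive DL3 | 40%, 66% | 0.264 | – |
| Expected DL1 | 0.75%, 1.5% | 0.00011 | 0.9776 |
| Expected DL2 | 1.5%, 3% | 0.00045 | 0.9555 |
| Expected DL3 | 3%, 5% | 0.0015 | – |

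The chance that fast-track ends at DL1–DL3 with both in the same single patient is:

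- Excessive: 0.029 + 0.639 × 0.125 + 0.639 × 0.375 × 0.264 = 0.029 + 0.080 + 0.063 = 0.172, about 17%.
- Expected: 0.00011 + 0.9776 × 0.00045 + 0.9776 × 0.9555 × 0.0015 = 0.0020, about 0.2%.

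Under independence these are upper bounds, because they ignore order: a DLT that comes before the event qualifies goes straight to Stage 2 under either text. Positive association would raise them. At the extreme where every patient with a DLT also has the event, the Excessive figure is 0.10 + 0.71 × 0.25 + 0.71 × 0.50 × 0.40 = 0.42. The Expected figure is 0.0075 + 0.985 × 0.015 + 0.985 × 0.97 × 0.03 = 0.051. Adding up to nine single patients at DL4, under independence, gives 19.5% and 2.6%. DL4 is left out of the main figure because up to nine patients are planned there anyway.

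**3. What the early exposure could mean.** The chance of at least one DLT in two added patients is 1 − (1 − d)². At Excessive rates this is 1 − 0.90² = 19% (DL1), 1 − 0.75² = 44% (DL2) and 1 − 0.60² = 64% (DL3). At Expected rates it is 1.5%, 3.0% and 5.9%.

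**4. Table 2 and MTD selection.** Table 2's N columns sum to 0 + 1 + 1 + 1 + 9 = 12 (Expected) and 3 + 6 + 9 + 5 + 1 = 24 (Excessive). The two-stage design was simulated with 3,000 trials per setting, a one-parameter power-model CRM with prior variance 1.34, and four assumed skeletons, because the plan defers the skeleton to Stage 2.

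- Expected: DL4 is chosen in 98–100% of trials (stated 100%).
- Excessive, from DL−1 to DL4: 1–5 / 14–21 / 42–59 / 21–31 / 1–6% (stated 3 / 18 / 44 / 34 / 1%).

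The shape matches, but Table 2 cannot be fully reproduced without the skeleton; that does not bear on this point. Run under the 6.2.1 rule and under the 13.1 rule, MTD selection differs by about 2 points or less.

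**The case against.** The best defence is that 13.1 cites 6.2.1, so a careful reader would apply the fuller rule, and that the two footnotes already follow it. Toxicity was expected to be slight, the Expected overlap is 0.2%, and the entry for Revision 3 in the Revision History reports no DLT from dose level 1 to 4. This stands as a limit on size. It does not remove the conflict: 13.1 states its own time of action in current text, and the footnotes give the branch but not when to act.

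A reader might infer more than the documents support:

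- **That 6.2.1 discards the signal whenever the patient stops treatment, and the next single patient goes one level up.** Only one dose falls in the DLT period, so stopping for progression or refusal does not by itself end observation. Section 6.6 sets an End of Treatment visit 3 weeks (±1 week) after the last dose, about Day 22 after a single dose, and Section 8.1 schedules AE assessment, blood count and metabolic panel there. Section 11.4 reviews every patient at 21 days. No text orders escalation in this case; the plan is silent. The real gap is narrower: withdrawn consent, loss to follow-up or death from disease. Its frequency cannot be derived, because the documents give no rate of early departure.
- **That this switch is the only protection.** A DLT also ends fast-track, and the 21-day review exists.
- **That a DLT after early expansion leaves a dead end.** This mixes 13.1's timing with a clause of 6.2.1. Sections 6.2.2 and 13.1 both send the first DLT during Step 2 to Stage 2.
- **That the MTD is biased.** The simulated comparison does not show it.

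**Conclusion.** The contradiction is real and should be corrected. Two texts wait for the DLT result, one does not, and the two footnotes side with the branch rule of the first two. Under 13.1 as written, two patients can be dosed before it is known whether Step 2 or Stage 2 applies.

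The size rests on Table 2's hypothesized rates, on reading its SAE column as the pre-defined event, on independence, and on the 5-day event window for the 13 to 18 days. On those terms at most about 17% of trials (Excessive) or 0.2% (Expected) would see both outcomes in the same single patient at DL1–DL3. The consequence is exposure and ambiguous conduct, with MTD selection essentially unchanged. With DL4 reportedly reached without a DLT, the correction now matters for remaining enrolment and for reporting which rule was applied.

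**What to change.** 1. Reconcile the Synopsis (Stage 1 Step 1), Section 6.2.1 and Section 13.1 to one activation condition and one activation time for Step 2. The time must be explicit: wording that only requires no DLT so far could already be met around Day 4 and would allow the same early start. Align the event window (5 or 21 days) in the same edit.
2. State how a dosed patient who has the event but whose DLT period cannot be completed counts for the trigger, and whether an End of Treatment assessment can close that period. The sponsor chooses the rule.
3. Confirm which version Table 2 simulated and say so beside footnote 1. The comparison above gives no reason to expect a material change in MTD selection.

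The cost is a few sentences of text, with no new visits, procedures or patients required by the reconciliation itself.

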# 6.2.2 STAGE 1 STEP 2 - Expand Current and Future DLs to 3 Patients

The cohort size increases from 1 to 3 patients with 2 additional patients added to the current cohort. A minimum of 21 days must separate each dose cohort. Continue dose escalation until:

- 1st DLT event Activate Stage 2 in Section 6.2.3.

  OR
- 9 patients are treated at the DL4 This completes enrollment and Stage 2 is not used.

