### 6.3 Monitoring for Dose Limiting Toxicities and Excessive Toxicity

Toxicity and adverse events are classified and graded according to NCI's Common Terminology Criteria for Adverse Events V 5.0 (CTCAE) unless otherwise noted in Section 10.

Note during the fast-track dose escalation only (Stage 1, Step 1), patients also are monitored for the pre-defined treatment emergent events defined in Section 6.2.1.

**Dose Limiting Toxicity (DLT)** is defined as any of the following treatment emergent adverse events using the NCI Common Terminology Criteria for Adverse Events (CTCAE) Version 5.0 within the 21 days after the 1st dose of HCW9218:

DLT event	Exceptions:		
Any Grade 3 or Grade 4 febrile neutropenia Any Grade 3 thrombocytopenia with bleeding Any Grade 3 or higher non-hematologic adverse event	
 
Grade 4 lymphopenia hat resolves to Grade 1 or lower (or to Baseline or lower, if pre-existing Grade 2 or higher) within 7 days
 
Grade 4 leukopenia that resolves to Grade 1 or lower (or to Baseline or lower, if pre-existing Grade 2 or higher) within 7 days
 
Grade 3 nausea, vomiting and/or diarrhea that last < 72 hours
 
Grade 3 or higher electrolyte abnormality that lasts < 72 hours, is not clinically complicated, and resolves spontaneously or responds to conventional medical interventions
 
Isolated Grade 3 elevation of ALT and/or AST that resolves to Grade 1 or lower (or to Baseline or lower, if pre-existing Grade 2 or higher) within 7 days
 
Grade 3 amylase or lipase that is not associated with symptoms or clinical manifestations of pancreatitis
 
		
	
 
Grade 3 fatigue, not due to disease progression, that lasts < 1 week
 
		
Hy's Law case (i.e., alanine aminotransferase/ aspartate aminotransferase (ALT/AST) >3 x ULN in combination with total bilirubin level (TBL) > 2 x ULN in the absence of cholestatic injury (ALP < 2 x ULN (Ricart, 2017; FDA, 2009)) and no other cause identified) after excluding biliary tract obstruction and liver metastasis  Inability to receive Cycle 2 dosing due to treatment related toxicity	MORE - I WOR		

The Dose Limiting Toxicity (DLT) Observation Period is defined as 21 days after the first dose of HCW9218. The DLT period does not end until the patient is assessed on Cycle 2 Day 1 (+3 days) and the results of lab work drawn on Cycle 2 Day 1 (+3 days) confirms no new DLTs since the previous assessment.

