- Cohort 4 is completed without a pre-defined AE or a DLT neither Step 2 nor Stage 2 is used if a total of 9 patients are enrolled in Cohort 4 to complete the study.

Stage 2 is initiated at the 1st DLT. The study design changes to an application of the continual reassessment method (CRM) with an informative skeleton based on constrained maximum likelihood estimation (lasonos & O'Quigley, 2012). Enrollment occurs in cohorts of three patients. Each new cohort of three patients are sequentially assigned to the most appropriate dose by the study statistician based on the updated toxicity probabilities once the 3rd patient in a cohort reaches Day 21 (DLT period). The goal will be to identify one of the 5 dose level strategies corresponding to the desired maximum toxicity rate of ≤25%. The MTD will be identified by the minimum of the following criteria: (1) the total Stage 2 sample size of 24 is exhausted or (2) 9 consecutive patients are enrolled at the same dose. The function 'crm' from the R package 'dfcrm' will calculate posterior means of toxicity probabilities. Dose escalation of more than one level is not permitted with this design.

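### Sections 6.2.1 and 6.2.2 complete enrolment once nine patients are treated at Dose Level 4, whereas 13.1 also requires no DLT, so a first DLT emerging after the ninth dosing meets two conflicting exits

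*Combined protocol and SAP*

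**What the plan says.** Section 6.2.1 (Stage 1 Step 1) lists exits joined by OR. One is a DLT: "1st DLT event within 21 days after the 1st dose of HCW9218" activates Stage 2. Another is a head count: "9 patients are treated at the DL4 - This completes enrollment - Stage 1 Step 2 and Stage 2 are not used". Section 6.2.2 (Step 2) has the same pair, a first-DLT exit and a nine-patient exit of which it says "This completes enrollment and Stage 2 is not used". The Synopsis enrolment plan repeats both. The head-count exit depends only on patients having been treated.

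Section 13.1 words the exit differently. For Step 2: "If Cohort 4 is completed without a DLT, Stage 2 (CRM) is not used". For Step 1, with nine patients in Cohort 4: "Cohort 4 is completed without a pre-defined AE or a DLT neither Step 2 nor Stage 2 is used". It then states "Stage 2 is initiated at the 1st DLT", with no exception for patients already dosed.

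Two other places fit 13.1. The Synopsis overview makes the Dose Level 4 expansion conditional on no DLT, and the Synopsis enrolment goal is 12, rising to at most 24 if a DLT is encountered.

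Section 6.3 sets the DLT period at 21 days from first dose and keeps it open until the Cycle 2 Day 1 assessment, which may fall up to three days late.

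**The concern.** A patient counts as treated on the day of injection but cannot be called DLT-free for at least 21 days. When the ninth Dose Level 4 patient is injected, the 6.2 exit is met while that patient, and any other still in the window, is unevaluated. If the first DLT of the trial then appears, the head-count exit says enrolment is over and the CRM is not used, while 13.1 says the CRM starts.

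Section 13.2 leaves the MTD to be settled by the design itself, so the enrolment rule is in effect the primary analysis. Under the 6.2 reading the late DLT updates no toxicity model, and the excessive-toxicity rule in 13.4 does not reach it because that rule covers Stage 2 only. In the extreme case of three late DLTs among nine (3/9 = 33%, against a 25% target), Stage 2 would still be unused. Under the 13.1 reading the trial continues in model-assigned cohorts, up to 24 patients in total.

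**Working it through.** **The plan's own figure.** One patient at each of Dose Levels 1 to 3 plus nine at Dose Level 4 gives 1 + 1 + 1 + 9 = 12. This matches the stated minimum and the Expected column of Table 2 (0 + 1 + 1 + 1 + 9 = 12). The nine-patient exit is therefore the path Table 2 expects.

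**How many patients are unevaluated at the ninth dosing.**
- Step 1: 13.1 asks for at least 21 days between patients until an exit is met, so essentially only the ninth is pending. The three-day allowance at Cycle 2 Day 1 could leave the eighth briefly open.
- Step 2: 13.1 separates three-patient cohorts by at least 21 days. If the nine enter as three cohorts of three (an assumption), up to three are pending.

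**Probability that the first DLT falls among the pending patients**, given that Dose Level 4 is reached without a DLT. Let p be the DLT rate at that level, with patients independent.
- One pending: (1 − p)^8 × p
- Three pending: (1 − p)^6 × [1 − (1 − p)^3]

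At p = 0.07 (Table 2, Expected):
- 0.93^8 × 0.07 = 0.039
- 0.93^6 × (1 − 0.93^3) = 0.647 × 0.196 = 0.127

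At p = 0.25 (the target ceiling):
- 0.75^8 × 0.25 = 0.025
- 0.75^6 × (1 − 0.75^3) = 0.178 × 0.578 = 0.103

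If the eighth patient is also open in Step 1, the 7% figure becomes 0.93^7 × (1 − 0.93^2) = 0.602 × 0.135 = 0.081.

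**Unconditionally, on the 1-1-1-9 path.** Table 2's Expected rates give no DLT at Dose Levels 1 to 3 with probability 0.9925 × 0.985 × 0.97 = 0.948, so the one-pending case is 0.948 × 0.0392 = 0.037. For context, the chance of no DLT in all 12 patients is 0.948 × 0.93^9 = 0.493. About half of such trials therefore meet a DLT, most of them before the ninth dosing, where the sections agree.

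**Effect on the result.** Both readings were simulated with 2,000 trials each, using an empiric CRM with a 25% target, prior variance 1.34 and a cap of 24 in total. Three skeletons were assumed, because the protocol gives none. Dose Level 4 patients entered in batches of up to three, so two or three were pending at the ninth dosing. That is more than 13.1's separation implies for Step 1.

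| Expected scenario | 6.2 reading | 13.1 reading |
|---|---|---|
| Stage 2 used | 42–44% | 51–52% |
| Mean N, Stage 1 patients not counted toward the nine-consecutive rule | 14.6–14.8 | 15.5–15.6 |
| Mean N, Stage 1 patients counted | 13.3–13.6 | 13.3–13.6 |
| Dose Level 4 selected | 99.3–99.6% | 99.3–99.7% |

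The conflict arose in 8–9% of Expected-scenario trials and in 0.2% or fewer of Excessive-scenario trials.

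**The case against.** The best defence is that 6.2 already contains the answer. Its first-DLT exit exempts neither Dose Level 4 nor the ninth patient, so a DLT on Day 15 in patient nine meets it. With the Synopsis overview and enrolment goal pointing the same way, the nine-patient bullet can be read as the residual no-DLT path, and *treated* as treated and evaluated. That may well be the intent, but the text does not say so and gives no precedence between the two exits. The defence does limit the point: a DLT seen before the ninth dosing is handled identically everywhere.

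Three stronger readings are tempting, and the documents do not support them.
- A reader might suppose that eight Dose Level 4 patients could be pending together, giving 0.93 × (1 − 0.93^8) = 41% at a 7% rate. The separation in 13.1 fits one pending patient in Step 1 and about three in Step 2.
- A reader might infer that the two readings usually yield different MTDs. In the simulation Dose Level 4 was selected in over 99% of Expected-scenario trials under both.
- A reader might infer that a late DLT would go unseen. Section 11.4 requires every patient's DLT status to be reviewed at 21 days, and Section 10.2 (footnote 3) has Stage 1 DLTs reported as contributing to later cohort decisions. The DLT would be recorded. What is missing under the 6.2 reading is a following cohort, a model update or a stopping rule for it to feed.

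**Conclusion.** The inconsistency is real and narrow. The nine-patient exit in 6.2.1, 6.2.2 and the Synopsis enrolment plan lacks the DLT-free condition that 13.1 imposes, and the two conflict only for a first DLT emerging after the ninth Dose Level 4 dosing. Given that Dose Level 4 is reached without a DLT, the chance is about 3.9% (Step 1) or 12.7% (Step 2) at a 7% rate, and 2.5% or 10.3% at 25%. These figures assume independent patients, 13.1's 21-day separation and, for Step 2, three cohorts of three.

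The expected effect on dose selection is small, although that finding rests on assumed skeletons. The case for change is that the rule producing the primary result should not give two instructions for the same event, and that under one of them a late DLT enters no model and falls outside the stopping rule.

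**What to change.** Reconcile the Synopsis enrolment plan (Stage 1 Steps 1 and 2), 6.2.1 and 6.2.2 with 13.1, so that one completion rule applies throughout. The reconciled text should:
- state that the nine-patient exit is judged only after all nine Dose Level 4 patients have completed the DLT period;
- state, consistently with 13.1, what a first DLT in any of the nine, including the last, triggers;
- align the Step 1 condition on pre-defined adverse events, which 13.1 has and the nine-patient exit in 6.2.1 lacks;
- say whether Dose Level 4 patients from Stage 1 count toward the rule of nine consecutive patients at one dose (6.2.3 and 13.1). If they do, a Stage 2 opened by a late DLT could close at once.

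The cost is a few wording edits and a wait of one DLT period after the last patient. In the minority of trials with a late first DLT, Stage 2 would open; averaged over simulated Expected-scenario trials this added less than one patient, and none if Stage 1 patients count toward the nine.
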